4 INVESTIGATIONAL PLAN

4.1 Overall Study Design and Plan

Study M16-852 is a Phase 3, global, multicenter, randomized, double-blind, PBO-controlled study. Approximately 420 subjects will be enrolled into this study.

The study population will consist of adult subjects who are at least 50 years of age with a diagnosis of active GCA, either new onset or relapsing disease, within 8 weeks of Baseline. Active GCA is defined by the presence of at least one of the following: unequivocal cranial symptoms of GCA, unequivocal symptoms of PMR, or other features judged by the investigator to be consistent with GCA or PMR flares, AND an ESR \geq 30 mm/hr or CRP \geq 1 mg/dL.

New onset disease is defined as diagnosis of GCA within 8 weeks of Baseline. Relapsing disease is defined as active GCA in a subject who has failed at least one attempted CS taper.

The study will allow enrollment of a minimum of 30% of subjects with new onset disease and up to 70% of subjects with relapsing disease. The study will also allow enrollment of up to 20% of subjects with previous use of an IL-6 inhibitor with discontinuation based on reasons other than disease flare.

The study duration will include a 35-day maximum Screening Period: a 52-week randomized, double-blind, parallel-group treatment period (Period 1); a 52-week blinded extension period in which subjects may either be re-randomized or continue their original treatment assignment (Period 2); and a 30-day follow-up period.

In Period 1, subjects who meet eligibility criteria will be randomized in a 2:1:1 ratio to 1 of 3 treatment groups:

- Upadacitinib 15 mg administered daily + 26-week CS taper regimen (n = 210)
- Upadacitinib 7.5 mg administered daily + 26-week CS taper regimen (n = 105)
- PBO administered daily + 52-week CS taper regimen (n = 105)

Subjects must have received treatment for active GCA at a dose of \geq 40 mg prednisone (or equivalent) at any time prior to Baseline and must be receiving prednisone (or prednisolone) \geq 20 mg QD at Baseline. Subjects must have GCA that, in the opinion of the investigator, is clinically stable to allow the subject to safely initiate the protocol-defined CS taper regimen.

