2.4 Sample Size Determination

[figure not shown]
The planned total sample size of 420 subjects with 2:1:1 ratio (upadacitinib 15 mg QD: upadacitinib 7.5 mg QD: Placebo QD) was determined to have at least 90% power to detect a 20% difference in sustained remission rate at Week 52 between the upadacitinib 15 mg arm and placebo arm (assuming a response rate of 40% in the placebo arm), using Fisher's exact test, with an overall two-sided alpha of 0.05.

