For the time to event endpoint (i.e., time to first disease flare), median time-to-event will be reported for each treatment group. Treatment comparisons in the distribution of time-to-event between each upadacitinib group and the placebo will be conducted using stratified log-rank test stratified by stratification factors. Median time for each treatment group will be provided based on Kaplan-Meier estimate. Subjects who never achieve the three criteria required before disease flare is considered (Section 9.4.1) during the treatment period will be censored at Baseline. Subjects who achieve the three criteria required before disease flare but never experience disease flare will be censored at the last assessment in Period 1. Analyses using Cox proportional hazards model with stratification factors as covariates will also be performed. Corresponding p-values, hazard ratios and 95% CIs will be reported.

For count endpoints (i.e., number of disease flare per subject and CS-related AEs), comparisons between each upadacitinib treatment group and the placebo group will be carried out using Poisson regression model with stratification factors as covariates, adjusted by the duration of study participation (or duration of study drug exposure for CS-related AEs). Log-transformation and robust standard error will be used in the Poisson regression model.

[figure not shown]
For all secondary binary endpoints (except for sustained complete remission and proportion of subjects who experience at least 1 disease flare), summary statistics will be provided for each treatment group using AO data. For all secondary continuous endpoints (except for cumulative CS exposure), an ANCOVA model will be applied based on AO data, with categorical fixed effects of treatment, stratification factors at randomization (Baseline CS dose [prednisone or prednisolone > 30 mg, prednisone or prednisolone ≤ 30 mg], and Baseline disease status [new onset disease, relapsing disease]), and the continuous fixed covariates of Baseline measurement (where applicable) in the model.

[figure not shown]
The attributes of the estimands corresponding to the multiplicity-controlled secondary efficacy objectives are summarized in Table 2.

Table 2. Summary of the Estimand Attributes Corresponding to the Multiplicity-Controlled Secondary Efficacy Endpoints

	Attributes of the Estimand					
Estimand Label	Treatment	Endpoint	Handling of Population Intercurrent Events		Statistical Summary	

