10.0 Safety Analyses

10.1 General Considerations

Unless otherwise specified, safety data will be summarized on SS1 for Period 1, SS2 for Period 2 and SS LT across Period 1 and Period 2. Safety analysis will include adverse events, laboratory, and vital signs measurements. Safety summaries will be presented by treatment group in each safety analysis set, including a total group for all subjects on active study treatment.

For the safety analysis, subjects are assigned to a treatment group based on the treatment actually received, regardless of the treatment randomized.

Missing safety data will not be imputed.

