10.3 Analysis of Laboratory Data

Selected clinical laboratory tests defined in the protocol operations manual (e.g., hematology, clinical chemistry) will be summarized on SS1 for Period 1 and SS LT for long term.

Baseline is defined as the last non-missing measurements recorded on or before the date of the first dose of study drug. For the analysis of laboratory data, values observed within 30 days of the last dose of study drug will be included.

Each laboratory variable will be summarized for all time points (starting with Baseline) with the number of non-missing observations, mean and standard deviation, median, minimum and maximum. Mean change from Baseline to each applicable post-baseline visit will be summarized for selected laboratory variables, with the number of observations, Baseline mean, and visit mean. In Period 1, mean change from Baseline will be compared between treatment groups using a one-way Analysis of Variance (ANOVA), with treatment as a fixed factor. The change from Baseline mean, standard error, and 95% confidence interval will be presented for the mean change from Baseline within each treatment group and difference between treatment groups.

[figure not shown]
Laboratory abnormalities will be evaluated based on Potentially Clinically Important (PCI) criteria (Appendix C). For each laboratory PCI criterion, the number and percentage

of subjects who have a laboratory value meeting the criteria will be summarized. Listings will be provided to summarize subject-level laboratory data for subjects meeting PCI criteria.

Changes in laboratory parameters will be tabulated using shift tables by National Cancer Institute (NCI) Common Terminology Criteria (CTC) (version 4.03). Selected lipid parameters will be summarized using National Cholesterol Education Program (NCEP) Adult Treatment Panel III (ATPIII) guidelines (Appendix D). A shift table from Baseline to the worse value during treatment will be created. A similar shift table will be provided to summarize shifts from Baseline to the final post-baseline value.

In addition, ALT/SGPT, AST/SGOT, alkaline phosphatase, and total bilirubin will be categorized as follows:

- ALT $> 3 \times ULN$
- ALT $> 5 \times ULN$
- $ALT > 10 \times ULN$
- $ALT > 20 \times ULN$
- $AST > 3 \times ULN$
- $AST > 5 \times ULN$
- AST $> 10 \times ULN$
- $AST > 20 \times ULN$
- $TBL > 2 \times ULN$
- Alkaline phosphatase (ALP) $> 1.5 \times ULN$
- ALT and/or AST $> 3 \times ULN$ and TBL $> 1.5 \times ULN$

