10.4 Analysis of Vital Signs

Vital sign measurements of systolic and diastolic blood pressure, pulse rate, respiratory rate, body temperature and weight will be summarized.

For the analysis of vital signs data, values observed within 30 days of the last dose of study drug will be included.

Each vital sign variable will be summarized for all time points (starting with Baseline) with the number of non-missing observations, mean and standard deviation, median, minimum and maximum. Mean change from Baseline to each applicable post-baseline visit will be summarized for each vital sign variable, with the number of observations, Baseline mean, and visit mean. In Period 1, mean change from Baseline will be compared between treatment groups using a one-way ANOVA, with treatment as a fixed factor. The change from Baseline mean, standard error, and 95% confidence interval will be presented for the mean change from Baseline within each treatment group and difference between treatment groups.

Vital sign variables will be evaluated based on PCI criteria (Appendix C). For each vital sign PCI criterion, the number and percentage of subjects who have a vital sign value meeting the criteria will be summarized. Listings will be provided to summarize subject-level vital sign data for subjects meeting PCI criteria.

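### Laboratory and vital-sign changes are compared by a valid one-way ANOVA that leaves out the baseline value and so gives up some precision

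*SAP*

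**What the plan says.** For laboratory data in Period 1, SAP 10.3 says that "mean change from Baseline will be compared between treatment groups using a one-way Analysis of Variance (ANOVA), with treatment as a fixed factor". For vital signs, SAP 10.4 says that "mean change from Baseline will be compared between treatment groups using a one-way ANOVA, with treatment as a fixed factor". Neither section names any other model term. Both sections report intervals between arms as well as within them; in 10.3, a "95% confidence interval will be presented for the mean change from Baseline within each treatment group and difference between treatment groups".

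The baseline value is available by definition: "Baseline is defined as the last non-missing measurements recorded on or before the date of the first dose of study drug". SAP 10.5 plans no further safety analyses, so no baseline-adjusted comparison of these variables appears elsewhere.

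Continuous efficacy endpoints are handled differently. The as-observed ANCOVA in SAP 9.4.2 has treatment, the stratification factors "and the continuous fixed covariates of Baseline measurement (where applicable) in the model". The MMRM in SAP 9.2 and the tipping-point ANCOVA in Appendix F also carry baseline.

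**The concern.** A change score subtracts the whole baseline value. Unless follow-up moves one-for-one with baseline, that subtraction is not the best use of it, and the leftover baseline variation goes into the residual. Two consequences follow. The between-arm intervals are generally wider than they need be. And if the arms happen to differ at baseline on a given variable, part of that difference appears in the observed contrast. Protocol 5.9 stratifies on corticosteroid dose, prior IL-6 inhibitor use and disease status (with no stratification in Japan), not on laboratory values or vital signs, so such differences can arise by chance.

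The variables are not incidental. Protocol 2.2 reports changes in transaminases, lipids, creatine phosphokinase, haemoglobin and white cells with upadacitinib, and Protocol 6.1 lists several related events as being of special interest. What is at stake is how sharply the mean shifts in such variables are estimated.

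**Working it through.** **Plan's own figure.** There is none for these comparisons. The only design figure is the power of the primary endpoint (SAP 2.4), which this model does not touch.

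**Inputs.** Planned arms are 210, 105 and 105 (Protocol 4.1; SAP 2.4: "The planned total sample size of 420 subjects with 2:1:1 ratio"). The baseline-to-follow-up correlation r, and the ratio k of follow-up SD to baseline SD, are not in the documents. Both are assumed below, with r from 0.3 to 0.9. Units are baseline SDs.

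**Residual variance.**

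- Change-score ANOVA: 1 + k² − 2rk, which is 2(1 − r) when k = 1.
- ANCOVA with baseline: k²(1 − r²), which is 1 − r² when k = 1.
- Difference between the two: (1 − rk)².

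The difference is a square, so in large samples ANCOVA is never less precise. The two are equal only when the slope rk is 1. With k = 1 the variance ratio is (1 + r)/2, and the SE ratio is its square root.

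**Results for k = 1.** The multiplier for 15 mg against placebo is √(1/210 + 1/105) = 0.1195. The half-width is 1.96 × residual SD × 0.1195.

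| r | SE ratio | SE reduction | ANOVA interval wider by | Half-width, ANOVA | Half-width, ANCOVA |
|---|---|---|---|---|---|
| 0.3 | 0.806 | 19.4% | 24.0% | 0.277 | 0.224 |
| 0.5 | 0.866 | 13.4% | 15.5% | 0.234 | 0.203 |
| 0.7 | 0.922 | 7.8% | 8.5% | 0.182 | 0.167 |
| 0.8 | 0.949 | 5.1% | 5.4% | 0.148 | 0.141 |
| 0.9 | 0.975 | 2.5% | 2.6% | 0.105 | 0.102 |

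For 7.5 mg against placebo the multiplier is √(2/105) = 0.138. At r = 0.5 the half-widths are 0.270 and 0.234. Arm sizes cancel from the ratio, so the 428 enrolled subjects reported in SAP 9.1 do not change it.

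**Checks.** Simulating the three-arm models gave mean SE ratios of 0.866 at r = 0.5 and 0.926 at r = 0.7, close to the formula. With unequal SDs (k from 0.8 to 1.5, r from 0.3 to 0.9) the ratio ran from 0.71 to 1.00. It was 1.00 at k = 1.25, r = 0.8, where the slope is exactly 1.

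**Chance imbalance.** A baseline difference d between arms shifts the observed change contrast by (slope − 1) × d. One standard error of d is 0.12 SD for 210 against 105. At slope 0.5 that moves the contrast by 0.5 × 0.12 = 0.06 SD in the direction opposite to d. With k = 1 and r = 0.5 the contrast's own standard error is also 0.12 SD, so the shift is half a standard error. This is the same quantity as the lost precision: at r = 0.5, the ANOVA variance of 1.00 is 0.75 (ANCOVA) plus 0.25 (the imbalance term). The planned standard error therefore already allows for it.

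**The case against.** The strongest case against is that nothing here is wrong. A reader might infer that unadjusted change scores bias the comparison through regression to the mean. The documents do not support that: the arms are randomised, regression to the mean acts on all of them alike, and it cancels in expectation. Only chance imbalance passes through, and the stated interval covers it. Missing values are a separate matter ("Missing safety data will not be imputed").

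A reader might also infer that safety signals would be missed. That too goes beyond the documents. These means lie outside the tested family in SAP 12.0 and have no sample-size basis or decision rule. The same variables are examined through potentially clinically important counts, shift tables, liver-enzyme categories and eDISH plots (10.3 and 10.4), and through events of special interest (10.2.6). None of these uses the ANOVA.

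Nor does the contrast with the efficacy models prove an oversight. The version history in SAP 13.0 shows that the safety ANOVA was revisited in the 2.0 draft, which is compatible with a deliberate choice of a simple model.

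Two smaller objections stand in part. The equal-SD, linear working is least secure for skewed variables such as transaminases and creatine phosphokinase, where outlying baselines can pull a linear adjustment. And an adjusted difference will not equal the difference between the displayed arm means. These points limit the importance of the change; they do not remove the gain.

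**Conclusion.** The point holds as one of efficiency. The planned comparison is valid and unbiased under randomisation, but less precise than the collected data allow, and it lets chance baseline imbalance into the observed contrast. With equal SDs and r assumed between 0.3 and 0.9, the avoidable part of the standard error is about 19% at the low end and 2.5% at the high end, and it is nil where the slope of follow-up on baseline is 1. The actual gain will differ by variable and cannot be fixed from the documents. No confirmatory conclusion, alpha or sample size is affected. Severity is low: a free improvement.

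**What to change.** In SAP 10.3 and 10.4, replace the one-way ANOVA for the between-group comparison with ANCOVA on change from Baseline, with treatment as factor and the baseline value of the same variable as covariate. Report adjusted mean differences with 95% CI. Keep the unadjusted baseline, visit and change means by arm as descriptive results, and footnote that the adjusted difference need not equal the difference between them.

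The cost is one covariate and a footnote. No new data are needed, and no subject is lost, because a change score already requires a baseline. Protocol 7.4 asks only that changes be summarised and prescribes no ANOVA, so a SAP edit is enough. It should be made before the Period 1 unblinding; if that has already happened, the adjusted results should be labelled as added afterwards.

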10.4 Analysis of Vital Signs

Vital sign measurements of systolic and diastolic blood pressure, pulse rate, respiratory rate, body temperature and weight will be summarized.

For the analysis of vital signs data, values observed within 30 days of the last dose of study drug will be included.

Each vital sign variable will be summarized for all time points (starting with Baseline) with the number of non-missing observations, mean and standard deviation, median, minimum and maximum. Mean change from Baseline to each applicable post-baseline visit will be summarized for each vital sign variable, with the number of observations, Baseline mean, and visit mean. In Period 1, mean change from Baseline will be compared between treatment groups using a one-way ANOVA, with treatment as a fixed factor. The change from Baseline mean, standard error, and 95% confidence interval will be presented for the mean change from Baseline within each treatment group and difference between treatment groups.

Vital sign variables will be evaluated based on PCI criteria (Appendix C). For each vital sign PCI criterion, the number and percentage of subjects who have a vital sign value meeting the criteria will be summarized. Listings will be provided to summarize subject-level vital sign data for subjects meeting PCI criteria.

10.5 Other Safety Analyses

No other safety analyses will be provided.

10.6 Safety Subgroup Analyses

TEAEs will be assessed by subgroups for SS1 and SS LT as follows:

- TEAEs Overview
- TEAEs by SOC and PT
- AESI Overview and Adverse Events of Bone Fracture and Retinal Detachment

The following subgroups will be assessed:

[figure not shown]
- Age Group 1 (< 65 years, \ge 65 years)
- Age Group 2 (< 65 years, \ge 65 and < 75 years, \ge 75 years)
- Sex (male, female)
- Race Group (White, Non-White)
- Nicotine User (Current, Past, Never)
- Baseline BMI Group ($< 25 \text{ kg/m}^2$, $\ge 25 \text{ kg/m}^2$ and $< 30 \text{ kg/m}^2$, $\ge 30 \text{ kg/m}^2$)
- Geographic Region (North America, Western Europe, Eastern Europe, Asia, Oceania)
- Baseline CS Dose ($> 30 \text{ mg}, \le 30 \text{ mg}$)
- Prior Use of IL-6 Inhibitor (Yes, No)

For the events of herpes zoster, additional sub-group analyses will be conducted for SS1 and SS LT for the following subgroups:

- Prior History of Herpes Zoster (Yes, No)
- Prior History of Herpes Zoster Vaccination (Yes, No)

11.0 Interim Analyses

An interim futility analysis will be conducted to assess the lack of efficacy. The interim analysis will occur once the first 140 subjects complete 24 weeks of treatment

(approximately 70 subjects in the 15 mg active treatment arm; 35 subjects in the 7.5 mg active treatment arm and 35 subjects in the placebo arm).

The interim futility analysis is based on the conditional power (with details given in Appendix E) of 15 mg dose group compared to placebo for proportion of subjects achieving sustained remission at Week 24 (defined as absence of GCA signs and symptoms from Week 12 through Week 24 and adherence to the protocol-defined CS taper regimen through Week 24). If the conditional power is below the pre-specified threshold of 15%, the entire study will stop; otherwise, the entire study will move forward without modification. Since the entire study will be either continued without modification or terminated based on the futility analysis results, there will be no alpha spending due to the futility analysis.

11.1 Data Monitoring Committee

An external data monitoring committee (DMC) composed of persons independent of AbbVie and with relevant expertise in their field will review unblinded safety data from the ongoing study. The primary responsibility of the DMC will be to protect the safety of the subjects participating in this study.

[figure not shown]
The DMC will review safety data of the first 80 enrolled subjects through 8 weeks of treatment to determine if there are any significant safety concerns that would warrant any study action. Thereafter, the DMC will review safety data on a regular basis and as needed based on the accumulating safety data and will provide recommendations to AbbVie.

A separate DMC charter describes the roles and responsibilities of the DMC members, frequency of data reviews, relevant data to be assessed, and general operations.

Since there are no efficacy analyses for early stopping, no alpha adjustment is needed.

12.0 Overall Type-I Error Control

The overall Type I error rate of the primary and the multiplicity-controlled secondary endpoints will be strongly controlled using a graphical multiplicity adjustment method.^{3,4}

Specifically, the primary and multiplicity-controlled secondary endpoints as specified in Section 3.1 and Section 3.2 will be tested in the order as specified below and will begin with testing the primary endpoint for upadacitinib 15 mg dose using α of 0.05. Continued testing will follow a pre-specified α transfer path which includes downstream transfer along the endpoint sequence within each dose as well as cross-dose transfer. Adjusted P values for the primary and multiplicity-controlled secondary endpoints will be provided based on the testing procedure.

The testing procedures are provided below in Figure 2 (for US/FDA regulatory purpose) and Figure 3 (for PMDA regulatory purpose). The arrows specify the α transfer paths. Once a null hypothesis of an endpoint is rejected (i.e., deemed significant) at its assigned significance level, its significance level will be transferred to subsequent endpoint(s) following the arrow(s). The numbers on the arrows denote the weights for transferring and (possibly) splitting significance levels. Specifically, the weight 1 and 1/2 denotes 100% and 50% transfer of significance level, respectively. The primary and multiplicity-controlled secondary endpoints (V1-V7 in Table 3) will be tested sequentially. The remaining multiplicity-controlled secondary endpoints will be grouped together (V8-H in Table 3) and tested using Hochberg procedure.

[figure not shown]

Table 3. List of Primary and Secondary Endpoints for Regulatory Purpose (FAS1)

Name	Variable			
V0	Proportion of subjects achieving sustained remission at Week 52			
V1	Proportion of subjects achieving sustained complete remission from Week 12 through Week 52			
V2	Cumulative CS exposure through Week 52			
V3	Time to first disease flare through Week 52			
V4	Proportion of subjects who experience at least 1 disease flare through Week 52			
V5	Proportion of subjects in complete remission at Week 52			
V6	Proportion of subjects in complete remission at Week 24			
V7	Change from Baseline in the 36-item Short Form Quality of Life Questionnaire (SF-36) Physical Component Score (PCS) at Week 52			
V8-H	 Number of disease flares per subject through Week 52 Change from Baseline in Functional Assessment of Chronic Illness Therapy-Fatigue (FACIT-Fatigue) at Week 52 Assessment of Treatment Satisfaction Questionnaire for Medication (TSQM) patient global satisfaction subscale at Week 52 Rate of CS-related AEs through Week 52 			

Figure 2. Graphical Multiple Testing Procedure for Regulatory Purpose (FAS1)

[figure not shown]
[figure not shown]
[figure not shown]

Figure 3. Graphical Multiple Testing Procedure for PMDA Regulatory Purpose (FAS1)

[figure not shown]

